# Statistical Analysis Plan

Study alias & e-track number(s): Flu CC-SUIV-AS03-001 (201598)

- To describe the anti-H2 and anti-H18 antibody levels:
  - *In samples from all subjects who received an adjuvanted vaccine in the CC-Pan H5N1-001, the Q-Pan H1N1-019, the Q-Pan H9N2-001 adult study cohorts and in the Q-Pan H5N1-AS03-21 pediatric study cohort at baseline (D0), post-dose 2 (D42) and final timepoint (for persistence)*
  - *In adult subject samples of the Q-Pan-005 study cohort at D0, D42, D182, D549, D591, and D729 for group C and at D182, D224, D549, D591, and D729 for group G*
  - *In adult subject samples of the H5N1-012 study cohort (groups VT/VT/12M and VT/IN/12M) at D0, D21, M12, M12+21 days, and M18*
  - *In adult subject samples of the FLU D-QIV-015 study cohort at baseline (D0) and D21*
- To describe the *vaccine heterosubtypic* virus MN antibody level
  - *In baseline (D0) and post-dose 2 (D42) samples from all subjects who received an adjuvanted vaccine in the adult CC-Pan H5N1-001, the Q-Pan H1N1-019, the Q-Pan H9N2-001 and the pediatric Q-Pan H5N1-AS03-21 study cohorts*
  - *In adult subject samples of the Q-Pan-005 study cohort at D0, D42, D549, and D591 for group C and at D182, D224, D549, and D591 for group G*
  - *In adult subject samples of the H5N1-012 study cohort (groups VT/VT/12M and VT/IN/12M) at D0, D21, M12, and M12+21 days*
  - *In adult subject samples of the FLU D-QIV-015 study cohort at baseline (D0) and D21*

## 3.2. Secondary objectives

*With respect to samples from the HA Group 1-related studies (i.e., with H1N1, H5N1 and H9N2 pandemic, and IIV4 seasonal, influenza vaccines):*

- To assess the effect of adjuvant in *the CC-Pan H5N1-001, the Q-Pan H1N1-019 and the Q-Pan H9N2-001 adult study cohorts* in terms of the adjusted anti-H1 stalk ELISA GMT ratio (AS group/no AS group) at D21, D42, D182, (for all 3 study cohorts) and D385 (for the *CC-Pan-H5N1-study cohort*), and in terms of the difference in percentage of subjects (AS group minus no AS group) with a  $\geq 4$ -fold rise from Day 0 to Day 21 and D42, D182, (for all 3 study cohorts) and D385 (*for the CC-Pan-H5N1-study cohort*)
- *To describe the baseline seropositivity (SP) by hemagglutination inhibition (HI) assay to the pandemic vaccine homologous virus for all subjects and the baseline SP by HI assay to A/California/7/09 (or a like virus) for subjects in the CC-Pan*

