## 6. STATISTICAL METHODS

All analyses will be descriptive.

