## 6.2.2. Between groups assessment

### 6.2.2.1. For adult H5N1, H9N2, and H1N1 study cohorts

- For each **Group 1-related** study and for anti-H1 stalk ELISA results for adult H5N1, H9N2 and H1N1 study cohort, if available:
  - The difference in percentage of subject with at least 4-fold increase at *all applicable timepoints (D21, D42, D182, and D385) for which data are available* compared to Day 0 (i.e. adjuvanted group minus non-adjuvanted group *within each study cohort*, and the asymptotic standardized 95% CI, will be computed for each study cohort, separately.
  - The adjusted GMT ratio (adjuvanted group to non-adjuvanted group *within each study cohort*) of anti-H1 stalk ELISA antibodies for adjuvanted vaccine over non-adjuvanted vaccine at all timepoints (D21, D42, D182, and D385) for which data are available and the two-sided 95% CI on each GMT ratio will be computed for each study cohort, separately. ANCOVA models on the logarithm10 transformation of the titers, including the vaccine group as fixed effect and age category (<30 years and >=30 years) and the anti-H1 stalk ELISA result at Day 0 as covariates.
- For H1N1 study cohort and for anti-N1 NA ELISA results, if available:
  - The difference in percentage of subject with at least 4-fold increase at all time points (D21, 42 and 182) compared to Day 0 (i.e. adjuvanted group minus non-adjuvanted group, and the asymptotic standardized 95% CI, will be computed.
  - The adjusted GMT ratio (adjuvanted group to non-adjuvanted group) of anti-N1 NA ELISA antibodies for adjuvanted vaccine over non-adjuvanted vaccine at all timepoints (D21, D42 and D182) for which data are available and the two-sided 95% CI on each GMT ratio will be computed. ANCOVA models on the logarithm10 transformation of the titers, including the vaccine group as fixed

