# Statistical Analysis Plan

Study alias & e-track number(s): Flu CC-SUIV-AS03-001 (201598)

of the assay will be given an arbitrary value of half the cut-off for the purpose of GMT calculation.

- The 95% CI for geometric mean titres (GMTs) will be obtained within each group separately. The 95% CI for the mean of log-transformed titre will be first obtained assuming that log-transformed values were normally distributed with unknown variance. The 95% CI for the GMTs will be then obtained by exponential-transformation of the 95% CI for the mean of log-transformed titre.
- Four-fold antibody titer increase is defined as post/pre for seropositive subjects; and post/half of the cut off value for seronegative subjects
- *Ten-fold antibody titer increase is defined as post/pre for seropositive subjects; and post/half of the cut off value for seronegative subjects*
- All CI computed will be two-sided 95% CI. The exact 95% CIs for a proportion within a group will be based on the method by Clopper [Clopper, 1934\*].

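### The difference in ≥4-fold rise has no adjustment for Day 0 titre, unlike the GMT ratio beside it; a prespecified baseline-adjusted difference would protect against chance imbalance at little cost

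*SAP*

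**What the plan says.** SAP Section 3.2 assesses the adjuvant effect in the three adult cohorts (H5N1, H1N1, H9N2) in two ways. One is "in terms of the adjusted anti-H1 stalk ELISA GMT ratio (AS group/no AS group"), the other "in terms of the difference in percentage of subjects (AS group minus no AS group) with a" ≥4-fold rise from Day 0. Section 4.2 lists both as secondary endpoints.

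Section 6.2.2.1 fixes the methods. The GMT ratio comes from an ANCOVA on log10 titre with vaccine group, age category "and the anti-H1 stalk ELISA result at Day 0 as covariates". For the percentage difference the SAP names only the subtraction, "and the asymptotic standardized 95% CI, will be computed for each study cohort, separately"; no covariate is mentioned. The same pairing is planned for anti-N1 NA in the H1N1 cohort (Section 6.2.2.1) and anti-H3 stalk in the H7N9 cohort (Section 6.2.2.2, where the ANCOVA has Day 0 titre but no age term).

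Section 7.1 defines the responder: "Four-fold antibody titer increase is defined as post/pre for seropositive subjects; and post/half of the cut off value for seronegative subjects". Section 2 matches unadjuvanted to adjuvanted subjects on age band and study centre, and Table 1 expects 20-30 per group. Section 6 states: "All analyses will be descriptive".

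**The concern.** Dividing by the subject's own Day 0 titre removes the influence of baseline only if log post-titre rises one-for-one with log Day 0 titre. The ANCOVA for the GMT ratio does not assume that; it estimates the slope. The responder comparison, on the same sera, in effect fixes the slope at 1. If the true slope is lower, subjects with high baselines find a 4-fold rise harder to reach, and a group that happens to start higher shows fewer responders for that reason alone.

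Nothing in the selection balances Day 0 stalk titre, and groups of 20-30 leave room for chance imbalance. Because there is no hypothesis test, the estimate and its interval are the whole result for this endpoint. At stake are an estimate displaced by an imbalance visible in the same tables, and precision lost by ignoring a covariate already used in the companion model.

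**Working it through.** **Inputs.** From the SAP: 20-30 per group, the 4-fold threshold, two-sided 95% intervals. The SAP gives no responder rate, titre SD, slope or sample-size figure for this comparison, so there is nothing of its own to reproduce. Assumed, with ranges: responders 50% (adjuvanted) and 30% (unadjuvanted) at balance; Day 0 SD (SD0) 0.4-0.5 log10; residual SD (s) 0.25-0.35; log10 fold rise falling by d = 0 to 0.6 per log10 of baseline (d = 1 minus the slope of post on Day 0).

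**Size of chance imbalance.** In units of SD0, the difference in mean Day 0 log titre has standard deviation √(2/n): 0.258 at n=30 and 0.316 at n=20.
- P(imbalance > 0.5 SD) = 2[1 − Φ(0.5/√(2/n))] = 5% at n=30, 11% at n=20.
- P(imbalance > 0.4 SD) = 12% and 21%.

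**Shift in the crude difference.** With log10 rise = group mean − d·(Day 0) + error, the SD of the log rise is r = √((d·SD0)² + s²). Let the adjuvanted group start k·SD0 higher, split equally between groups. Each group's z-value then moves by h = d·k·SD0/(2r), and the expected difference is Φ(0 − h) − Φ(−0.524 + h). At k = 0.5:

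| d | SD0 | s | r | h | Expected difference | Shift (points) |
|---|---|---|---|---|---|---|
| 0 | 0.45 | 0.30 | 0.300 | 0 | 50.0 − 30.0 = 20.0 | 0 |
| 0.2 | 0.40 | 0.35 | 0.359 | 0.056 | 47.8 − 32.0 = 15.8 | −4.2 |
| 0.4 | 0.45 | 0.30 | 0.350 | 0.129 | 44.9 − 34.6 = 10.3 | −9.7 |
| 0.6 | 0.50 | 0.25 | 0.391 | 0.192 | 42.4 − 37.0 = 5.4 | −14.6 |

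Simulation over the same ranges with true differences of 20-24 points gave 4.1 to 14.0 points. A typical imbalance of 0.258 SD (one standard deviation at n=30) gives about 2 to 7 points.

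**Against sampling error.** The Wald half-width is 1.96·√((0.5·0.5 + 0.3·0.7)/n) = 24 points at n=30 and 30 at n=20.

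**Average behaviour.** Simulated at n=30 with a true difference of 0.20, the crude difference averaged 0.20 at every slope. Overall Wald coverage was 94% at n=30 and 93% at n=20, including at zero decline.

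**What adjustment changes.** A logistic model standardised over both groups was simulated with SD0 0.45, s 0.3 and responders 50% vs 30%:
- adjusted coverage 93-95%;
- SD at n=30 lower by about 2% (d = 0.2) to 14% (d = 0.6), and at most 2% higher when d = 0;
- among samples with imbalance above 0.4 SD at n=30, crude coverage 84-92% against 93-95% adjusted, for d of 0.2-0.6.

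**Where it fails.** The model failed in 11-27% of simulated runs when one group had few responders. The reason is simple: at a true rate of 5%, a group has no responder at all with probability 0.95^30 = 21% at n=30 and 0.95^20 = 36% at n=20.

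**The case against.** The other side has a good deal that stands.

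- A reader might infer that the SAP contradicts itself. It does not. Section 3.2 attaches the word adjusted only to the GMT ratio, and Sections 4.2, 6.2.2.1 and 6.2.2.2 carry the crude difference through consistently.
- A reader might infer that the crude difference is biased. Averaged over samples it is not: the primary studies were randomised, and nothing in the SAP ties selection to Day 0 stalk titre. The displacement exists only given an observed imbalance, and the low coverage figures describe only the 12% of samples at n=30 with the larger imbalances.
- A reader might blame baseline for any disagreement between the two measures. Much of it comes from dichotomising. In simulation at n=30 (SD0 0.4, s 0.35, 50% vs 30%) the two intervals disagreed on excluding no effect in 24% of runs at d = 0, where imbalance plays no part, and in 38% at d = 0.6. Opposite directions occurred in 3-4% of runs at every slope.
- The analyses are descriptive and no decision rests on the endpoint. Day 0 GMTs and seropositivity by group (Section 4.1) and the reverse cumulative curves (Section 6.2.1) will show an imbalance.
- The fall in fold rise with baseline is an assumption, and typical shifts lie well inside the interval.

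These points rule out calling the crude analysis invalid or replacing it. They do not remove the case for an adjusted companion: showing an imbalance does not correct for it, and the covariate is already in the model next door.

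**Conclusion.** The point holds as a specific, inexpensive improvement in analysis choice. The secondary-endpoint difference in ≥4-fold rise, and its tertiary counterparts for anti-N1 NA and anti-H3 stalk, ignore a baseline that the paired GMT ratio uses.

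If fold rise declines with baseline by 0.2-0.6 per log10, a 0.5 SD imbalance moves the estimate by about 4-14 points toward the group with the lower baseline; at zero decline the shift is nil. Such an imbalance is exceeded in about 5% of comparisons at n=30 and 11% at n=20. The precision forgone is about 0-15% in SD. Every input except group size is assumed, so these figures give a plausible range and do not predict what the trial will show. The documents support neither a claim of average bias nor one of internal contradiction.

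**What to change.** In Sections 6.2.2.1 and 6.2.2.2, keep the crude difference with its asymptotic standardized interval, and prespecify beside it a baseline-adjusted difference in ≥4-fold rise for anti-H1 stalk, anti-N1 NA and anti-H3 stalk. Use logistic regression with the terms of the corresponding ANCOVA: vaccine group, log10 Day 0 titre, and age category where the ANCOVA has it. Standardise the predictions over both groups to a marginal percentage difference with 95% CI.

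State the sparse-data rule in advance rather than switching on non-convergence. For example, set a minimum number of responders and of non-responders per group; below it, report a difference stratified at the cohort's median Day 0 titre, or the crude difference alone.

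The cost is SAP wording and a few lines of SAS, with no new samples or assays. Two small downsides: sparse timepoints will need the fallback, and the adjusted figure will not equal the subtraction of the two tabulated rates, which a table footnote should say.

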# Statistical Analysis Plan

Study alias & e-track number(s): Flu CC-SUIV-AS03-001 (201598)

*H5N1-001, Q-Pan H9N2-001, Q-Pan-005, and H5N1-012 study cohorts (baseline will be Day 0, but for group G of the Q-Pan-005 study cohort only, baseline will be Day 182)*

### 3.3. Tertiary objective

*With respect to samples from the HA Group 1-related studies (i.e., with H1N1, H5N1 and H9N2 pandemic, and IIV4 seasonal, influenza vaccines):*

- To describe the anti-N1 NA ELISA antibody levels at D0, D21, D42, and D182 for subjects **in the Q-PAN-H1N1-019 study cohort**, by treatment group
- To assess the effect of adjuvant in the **Q-PAN-H1N1-019** study cohort in terms of the adjusted anti-N1 NA ELISA GMT ratio (AS group/no AS group) at D21, D42, D182, and in terms of the difference in percentage of subjects (AS group minus no AS group) with a  $\geq 4$ -fold rise from Day 0 to Day 21 and D42, D182.
- To explore the correlation between the level of neutralizing antibody to the H1 stalk with the level of vaccine homologous neutralizing antibody, at Day 0 and 21 in the adult **Q-Pan-H9N2-001 and CC-Pan-H5N1-001 study cohorts and in the pediatric Q-Pan H5N1-AS03-021** study cohorts (AS group only)
- To explore the effect of being seropositive by HI test to the vaccine homologous virus at D0 on the MGI (D21/D0) of anti-H1 stalk ELISA antibody in the adult H5N1, H9N2 and H1N1 study cohorts
- To explore the cell mediated immune response to H9N2 vaccine with respect to T cells, B memory cells and plasmablasts reactive with H9N2 and related antigens at Days 0, 7, 21, and 28 in selected vaccine groups **of the Q-Pan-H9N2-001 study cohort**
- To further characterize the humoral immune response to H9N2 vaccine **in the Q-Pan-H9N2-001 study cohort** by ELISA using the purified recombinant viral proteins (H9 HA head domain, H9 full length, N2)

*With respect to samples from the HA group 2-related study cohort (H7N9 study) (adult subjects):*

- **To describe the anti-H3 stalk ELISA antibody levels:**
  - *At baseline Day 0 (D0), post-dose 1 at Day 21 (D21), post-dose 2 at Day 42 (D42), Month 6, and Month 12 by treatment group (unadjuvanted or adjuvanted vaccine), from the primary completed H7N9 study*
- **To describe the anti-H3 stalk microneutralization (MN) antibody levels (target virus: cH14/3Nx):**
  - *At baseline Day 0 (D0), post-dose 1 at Day 21 (D21), post-dose 2 at Day 42 (D42), Month 6, and Month 12 for subjects who received adjuvanted vaccine*

# Statistical Analysis Plan

Study alias & e-track number(s): Flu CC-SUIV-AS03-001 (201598)

- *To describe the anti-H4 and anti-H10 antibody levels at baseline (D0), post-dose 2 (D42), and Month 12 (for persistency) in all subjects from the H7N9 study cohort who received an adjuvanted vaccine*
- *To describe the heterosubtypic virus MN antibody level (target virus: H4N8) at baseline (D0) and post-dose 2 (D42) in all subjects who received an adjuvanted vaccine*
- *To assess the effect of adjuvant in the adult H7N9 study cohort in terms of the adjusted anti-H3 stalk ELISA GMT ratio (AS group/no AS group) at D21, D42, Month 6, and Month 12, and in terms of the difference in percentage of subjects (AS group minus no AS group) with a  $\geq 4$ -fold rise from Day 0 to Day 21 and D42, Month 6, and Month 12*

*Please note that the tertiary objectives related to mice experiment will be presented in separate SAP as it will be performed by pre-clinical statistical team.*

## 4. ENDPOINTS

### 4.1. Primary endpoints

*With respect to samples from the HA Group 1-related studies (i.e., with H1N1, H5N1, and H9N2 pandemic, and IIV4 seasonal, influenza vaccines):*

1. Levels of anti-H1 stalk antibody by ELISA for all the subjects in each study cohort. The following aggregate variables will be calculated with 95% CI for each treatment group within each study cohort:
  - For adult subject samples *from the CC-Pan H5N1-001, Q-Pan H1N1-019, and Q-Pan H9N2-001 study cohorts*:
    - Seropositive rate at Day 0, 21, 42, and 182 (and at Day 385 for H5N1 study cohort only)
    - Geometric mean titer (GMT) at Day 0, 21, 42, and 182 (and at Day 385 for H5N1 study cohort only)
    - Percentage of subjects with a  $\geq 4$ -fold rise from Day 0 to Day 21 *and from Day 0 to Day 42*
    - *Percentage of subjects with a  $\geq 10$ -fold rise from Day 0 to Day 21 and from Day 0 to Day 42*
    - Mean geometric increase (MGI) at Day 21, 42, and 182 (and at Day 385 for H5N1 study cohort only) compared to Day 0
  - For pediatric subject samples *from the Q-Pan H5N1-AS03-21 cohort*:
    - Seropositive rate at Day 0, 21, 42 and at Day 385

# Statistical Analysis Plan

Study alias & e-track number(s): Flu CC-SUIV-AS03-001 (201598)

- Geometric mean titer (GMT) at Day 0, 21, 42 and at Day 385
- Percentage of subjects with a  $\geq 4$ -fold rise from Day 0 to Day 21 ***and from Day 0 to Day 42***
- ***Percentage of subjects with a  $\geq 10$ -fold rise from Day 0 to Day 21 and from Day 0 to Day 42***
- Mean geometric increase (MGI) at Day 21, 42 and at Day 385 compared to Day 0
- ***For adult subject samples from the Q-Pan-005 study cohort, groups C and G:***
  - ***Seropositive rate at Day 0, 42, 182, 224, 549, 591, and at Day 729***
  - ***Geometric mean titer (GMT) at Day 0, 42, 182, 224, 549, 591, and at Day 729***
  - ***Percentage of subjects with a  $\geq 4$ -fold rise***
    - ***For group C: From Day 0 to Day 42, from Day 549 to Day 591 and from Day 0 to Day 591***
    - ***For group G: From Day 182 to Day 224, from Day 549 to Day 591 and from Day 182 to Day 591***
  - ***Percentage of subjects with a  $\geq 10$ -fold rise***
    - ***For group C: From Day 0 to Day 42, from Day 549 to Day 591 and from Day 0 to Day 591***
    - ***For group G: From Day 182 to Day 224, from Day 549 to Day 591 and from Day 182 to Day 591***
  - ***Mean geometric increase (MGI) at Day 42, 182, 224, 549, 591, and at Day 729 compared to Day 0 for group C and for Day 224, 549, 591 and Day 791 compared to Day 182 for group G***
- ***For adult subject samples from the H5N1-012 study cohort (groups VT/VT/12M and VT/IN/12M):***
  - ***Seropositivity rate at Day 0, 21, M6, M12, M12+21days and M18***
  - ***GMT at Day 0, 21, M6, M12, M12+21days, and M18***
  - ***Percentage of subjects with a  $\geq 4$ -fold rise from Day 0 to Day 21, from M12 to M12+21days, and from Day 0 to M12+21days***
  - ***Percentage of subjects with a  $\geq 10$ -fold rise from Day 0 to Day 21, from M12 to M12+21days, and from Day 0 to M12+21days***
  - ***MGI at Day 0, 21, M6, M12, M12+21, and M18***
- ***For adult subject samples from the FLUD-QIV-015 study cohort:***

# Statistical Analysis Plan

Study alias & e-track number(s): Flu CC-SUIV-AS03-001 (201598)

- *Seropositive rate at Day 0 and 21*
  - *Geometric mean titer (GMT) at Day 0 and 21*
  - *Percentage of subjects with a  $\geq 4$ -fold rise from Day 0 to Day 21*
  - *Mean geometric increase (MGI) at Day 21 compared to Day 0*
- 2. Levels of anti-H1 stalk antibody by microneutralization (MN) for the subjects who received an adjuvant system (AS) vaccine in each study cohort. The following aggregate variables will be calculated with 95% CI:
  - For adult subject samples from the ***CC-Pan H5N1-001, Q-Pan H1N1-019, and Q-Pan H9N2-001 study cohorts:***
    - Seropositive rate at Day 0, 21, 42, and 182 (and at Day 385 for H5N1 study cohort only)
    - Geometric mean titer (GMT) at Day 0, 21, 42, and 182 (and at Day 385 for H5N1 study cohort only)
    - Percentage of subjects with a  $\geq 4$ -fold rise from Day 0 to Day 21 ***and from Day 0 to Day 42***
    - *Percentage of subjects with a  $\geq 10$ -fold rise from Day 0 to Day 21 and from Day 0 to Day 42*
    - Mean geometric increase (MGI) at Day 21, 42, and 182 (and at Day 385 for H5N1 study cohort only) compared to Day 0
  - For pediatric subject samples from the ***Q-Pan H5N1-AS03-21 study cohort:***
    - Seropositive rate at Day 0, 21, 42 and at Day 385
    - Geometric mean titer (GMT) at Day 0, 21, 42 and at Day 385
    - Percentage of subjects with a  $\geq 4$ -fold rise from Day 0 to Day 21 ***and from Day 0 to Day 42***
    - *Percentage of subjects with a  $\geq 10$ -fold rise from Day 0 to Day 21 and from Day 0 to Day 42*
    - Mean geometric increase (MGI) at Day 21, 42 and at Day 385 compared to Day 0
  - ***For adult subject samples from the Q-Pan-005 study cohort:***
    - *Seropositive rate at Day 0, 42, 182, 549, 591 and 729 for group C and at Day 182, 224, 549, 591 and 729 for group G*
    - *Geometric mean titer (GMT) at Day 0, 42, 182, 549, 591 and 729 for group C and at Day 182, 224, 549, 591 and 729 for group G*
    - *Percentage of subjects with a  $\geq 4$ -fold rise*

# Statistical Analysis Plan

Study alias & e-track number(s): Flu CC-SUIV-AS03-001 (201598)

- *For group C: From Day 0 to Day 42, from Day 549 to Day 591 and from Day 0 to Day 591*
    - *For group G: From Day 182 to Day 224, from Day 549 to Day 591 and from Day 182 to Day 591*
    - *Percentage of subjects with a  $\geq 10$ -fold rise*
      - *For group C: From Day 0 to Day 42, from Day 549 to Day 591 and from Day 0 to Day 591*
      - *For group G: From Day 182 to Day 224, from Day 549 to Day 591 and from Day 182 to Day 591*
    - *Mean geometric increase (MGI) at Day 42, 182, 549, 591 and 729 compared to Day 0 for group C and at Day 224, 549, 591 and 729 compared to Day 182 for group G*
  - *For adult subject samples from the H5N1-012 study cohort (groups VT/VT/12M and VT/IN/12M):*
    - *Seropositivity rate at Day 0, 21, M6, M12, M12+21days, and M18*
    - *GMT at Day 0, 21, M6, M12, M12+21days, and M18*
    - *Percentage of subjects with a  $\geq 4$ -fold rise from Day 0 to Day 21, from M12 to M12+21days, and from Day 0 to M12+21days*
    - *Percentage of subjects with a  $\geq 10$ -fold rise from Day 0 to Day 21, from M12 to M12+21days, and from Day 0 to M12+21days*
    - *MGI at Day 0, 21, M6, M12, M12+21, and M18*
  - *For adult subject samples from FLUD-QIV-015 cohort:*
    - *Seropositive rate at Day 0 and 21*
    - *Geometric mean titer (GMT) at Day 0 and 21*
    - *Percentage of subjects with a  $\geq 4$ -fold rise from Day 0 to Day 21*
    - *Mean geometric increase (MGI) at Day 21 compared to Day 0*
3. Levels of anti-H2 and anti-H18 antibody by ELISA for the subjects who received an AS vaccine *in each* study cohort *and for the subjects in the FLUD-QIV-015 study cohort*. The following aggregate variables will be calculated with 95% CI:
- *For samples from subjects in the adult CC-Pan H5N1-001, Q-Pan H1N1-019, Q-Pan H9N2-001 and pediatric Q-Pan H5N1-AS03-21 study cohorts:*
    - Seropositive rate at Day 0, 42, *and final timepoint (for persistence) (i.e., Day 182 for the Q-Pan-H1N1-019, Q-PAN-H9N2-001 and Day 385 for the CC-Pan-H5N1 and Q-Pan H5N1-AS03-21 study cohorts)*

